Aim 1: To compare the non-invasive hemodynamic measurements of cardiac output, stroke volume, and heart rate between a validated reference tool (i.e. echocardiogram) and the NICOM in pregnant women with structurally normal and abnormal hearts (in the first, second, and third trimesters, intrapartum and postpartum).

Aim 2: Assess the precision and accuracy of heart rate, stroke volume and cardiac output of the NICOM machine. The purpose of this study is to establish validity and clinical utility of the NICOM machine in women with structural cardiac disease in labor, which can further guide management while avoiding invasive (monitoring) procedures.

Our hypothesis is that there is acceptable correlation between NICOM and ECHO in cardiac output, stroke volume, blood pressure and heart rate with a mean percentage difference of < 30% throughout pregnancy (it has been proposed that a MPD of 30% between two methodologies is clinically acceptable for CO estimation). We expect the hemodynamic measurements of the NICOM machine will be within an acceptable mean percentage difference (clinically) to the measurements obtained by the echocardiogram. We will likely need to adjust for the increasing volume throughout gestation as a correction factor.

Analysis: An accepted "gold standard" for hemodynamic monitoring in women with both healthy and diseased hearts is not currently available. Pregnancy is associated with significant hemodynamic changes, both during and following delivery, which can be even more profound in the structurally-abnormal heart. Clinical

management of these women is based on surrogate markers of cardiac indices such as peripheral blood pressure, heart rate and oxygen saturation, rather than the use of invasive testing due to its associated complications. Echocardiography has largely replaced PAC in the obstetric population to measure cardiac output due to its non-invasive nature and good correlation with PAC¹⁸. However, its use is limited in the intrapartum period due to the need for clinical expertise in obtaining and interpreting the images. The proposed study has the potential to validate bio-reactance cardiac output monitoring using the NICOM against echocardiography for use in structurally abnormal pregnant hearts in order to better drive goal-directed (specifically delivery mode) therapy through continuous hemodynamic monitoring during the second and third stages of labor, and 24 hours postpartum.

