Statistical analysis will be carried out using R statistical package. We will perform Shapiro-Wilks to assess normality of the data. Correlation between the two methods will be assessed using either Pearson's (for normally distributed data) or Spearman (for non-normally distributed data) correlation coefficients. We will assess accuracy and precision by evaluating bias (mean difference between methodologies), the standard deviation of the differences, 95% limits of agreement (LOA=bias \pm 1.96 SD) and mean percentage differences (=LOA/mean of two methodologies). Bland-Altman plots will be constructed to compare the two measurement techniques. We will evaluate the inter-and intra-observer reproducibility by intraclass correlation coefficients (ICC).

There will be no interim analysis since this is a non-inferiority trial comparing two diagnostic techniques, one of which is the is clinically-known to be equivalent to pulmonary artery catheterization (gold standard). Women will be recruited in the Maternal-Fetal Medicine office at their routine obstetrical visits. There will be no randomization as this will be an open-label, prospective study with each patient undergoing evaluation utilizing both diagnostic techniques. Statistical analysis will be carried out using R statistical package. We will perform Shapiro-Wilks to assess normality of the data. Correlation between the two methods will be assessed using either Pearson's (for normally distributed data) or Spearman (for non-normally distributed data) correlation coefficients. We will assess accuracy and precision by evaluating bias (mean difference between methodologies), the standard deviation of the differences, 95% limits of agreement (LOA=bias \pm 1.96 SD) and mean percentage differences (=LOA/mean of two methodologies). Bland-Altman plots will be constructed to compare the two measurement techniques. We will evaluate the inter-and intra-observer reproducibility by intraclass correlation coefficients (ICC).

Data Management, Security, Confidentiality, and Safety

The primary investigator and the co-investigators will have access to the study data. The controls will only be accessed by this aforementioned group of researchers. As the study group's care will not be altered from a clinical standpoint, any provider that usually has access to the patient record will be able to view the imaging/documentation as clinically indicated in EPIC.

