We will limit the data collection to physicians and nurses trained in data collection (the aforementioned PI and co-investigators). The cardiac imaging will be read by board-certified cardiologists. The maternal-fetal medicine physicians will be trained by the NICOM company in proper placement of the NICOM leads and will be the only personelle applying the NICOM pads. The data from the NICOM will be collected only by the PI who is trained in the NICOM system.

Each echocardiogram will be reviewed by a board-certified cardiologist after each study has been completed. In the event there are any abnormalities, they will be discussed with the patient in detail and a management plan will be devised. There will be no interim analysis during this study. The data will be analyzed under the analytics and statistical section.

As this is a non-inferiority trial comparing two diagnostic techniques, we do not foresee any triggers that would cause the study to stop or be altered. In the event one of the control subjects is found to have a structural cardiac anomaly, we will treat her according to the standard of care for that particular disease state.

The risk of harm during this study is minimal and therefore we do not anticipate any adverse events. We will perform a thorough history and physical exam at the initial OB visit to assess the patient's eligibility and willingness to participate. If at that time she is found to have allergies to adhesive or conductance gel, we can use alternative measures (i.e. non-adhesive pads, latex-free conductance pad, lotion instead of conductance gel) to perform the procedure. If at any point we deem the risk is greater than minimal, we will not ask that

patient to participate in the study. Any unanticipated problem will be reported to the PI. At that point, we will have the study co-investigators discuss the issue with the PI and come up with a solution as a team. If the risk or event is deemed serious, it will be reported to the IRB within 2-3 days (depending on if it is a weekend).

If a patient does experience (what is deemed to be) an adverse event, she will be asked to leave the study. The results of the study will be shared via a peer-reviewed journal.

Consent Process

Once it has been established that the patient is willing to participate and has met inclusion criteria, any one of the co-investigators or the PI will approach the patient and review the consent in detail.

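### The mean percentage difference is defined so that it yields two values, while the hypothesis tests one value against 30%; the 30% is also applied beyond cardiac output, the only parameter the protocol supports it for

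*Combined protocol and SAP*

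**What the plan says.** The hypothesis, which follows Aim 2, expects "acceptable correlation between NICOM and ECHO in cardiac output, stroke volume, blood pressure and heart rate with a mean percentage difference of < 30" per cent throughout pregnancy. Its parenthesis gives the support for the threshold: it has been proposed that "a MPD of 30% between two methodologies is clinically acceptable for CO estimation". The same paragraph adds "We will likely need to adjust for the increasing volume throughout gestation as a correction factor".

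The Statistical Analysis section lists bias, "the standard deviation of the differences, 95% limits of agreement (LOA=bias" ± 1.96 SD), and then "mean percentage differences (=LOA/mean of two methodologies"). The text appears twice in identical words. It does not say which part of the LOA is the numerator, and it does not mention the correction factor.

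Background quotes an earlier third-trimester mean percentage difference (MPD) as one number, 32%, and calls it nearly acceptable. It also says that NICOM overestimated stroke volume and CO against echocardiography in the second trimester.

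The sample-size paragraph in Design sets a 0.5 L limit of bias for CO and powers the study on an absolute mean CO difference below 1.0 L, with 38 patients per arm. The Statistical Analysis and Data Management sections both describe the study as a non-inferiority trial ("As this is a non-inferiority trial comparing two diagnostic techniques").

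Aim 1 covers CO, stroke volume and heart rate. So does Aim 2: "Assess the precision and accuracy of heart rate, stroke volume and cardiac output of the NICOM machine". Blood pressure appears in neither.

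**The concern.** The 30% criterion is the only numerical threshold in the stated hypothesis, so its statistic should have one value that is fixed before data are seen. As written, LOA is a pair of limits, and dividing a pair by a mean gives a pair. An analyst must choose what to compare with 30%, and when bias is not zero that choice can decide whether the hypothesis is met. Background gives reason to expect some bias, though not its size.

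The second issue is scope. A threshold supported for CO is carried over to three other parameters without argument. For blood pressure there is also nothing to compare NICOM with: no reference measurement is described, and Design says that after the first trimester the control-group echocardiograms assess only CO and the left ventricular outflow tract.

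**Working it through.** **The plan's own figures.** The 30% is a criterion, so there is no calculation to reproduce. The 38 per arm cannot be confirmed or refuted, because neither the SD of the differences nor alpha is stated. It does not use the MPD.

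**Inputs.** From the documents: LOA = bias ± 1.96 SD; MPD = LOA/mean; threshold 30%; bias limit 0.5 L. Assumed: mean CO 5 to 8 L/min and a range of SDs.

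**Step 1: the two credible readings.**
- Half-width: 1.96 SD/mean.
- Larger limit: (|bias| + 1.96 SD)/mean. This follows if both limits must lie within ±30%.
- Difference between them: |bias|/mean.

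**Step 2: where the verdicts differ.** The larger limit is below 30% when SD < (0.3 × CO − |bias|)/1.96. The half-width is below 30% when SD < 0.3 × CO/1.96. Between these two SDs the verdicts are opposite. At bias 0.5 L:

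| Mean CO (L/min) | Difference (points) | Larger limit passes below SD (L) | Half-width passes below SD (L) |
|---|---|---|---|
| 5 | 0.5/5 = 10.0 | 1.0/1.96 = 0.51 | 1.5/1.96 = 0.77 |
| 6 | 0.5/6 = 8.3 | 1.3/1.96 = 0.66 | 1.8/1.96 = 0.92 |
| 7 | 0.5/7 = 7.1 | 1.6/1.96 = 0.82 | 2.1/1.96 = 1.07 |
| 8 | 0.5/8 = 6.3 | 1.9/1.96 = 0.97 | 2.4/1.96 = 1.22 |

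Example at CO 6, bias 0.5, SD 0.75: the half-width is 1.47/6 = 24.5%, a pass; the larger limit is 1.97/6 = 32.8%, a fail.

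**Step 3: smaller bias.** At CO 6 and bias 0.25 L the difference is 0.25/6 = 4.2 points, and the window narrows to (1.8 − 0.25)/1.96 = 0.79 up to 0.92 L. At zero bias the two readings coincide. For scale, Background's 32% is 2 points from the threshold; at CO 6 a bias of 0.02 × 6 = 0.12 L already separates the readings by that much.

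**Step 4: SDs that the sample size could imply.** Assume a paired test with margin 1.0 L, n = 38, 90% power and one-sided alpha of 2.5% or 5%. Then SD = (1 − d) × √38/(z_alpha + 1.2816), where d is the true difference.
- d = 0.5 L: SD 0.95 or 1.05. With bias 0.5 L, both readings fail at CO 5 and 6. At CO 7 they disagree (26.6% against 33.7% at SD 0.95; 29.4% against 36.5% at SD 1.05). At CO 8 both pass at SD 0.95 (23.3% and 29.5%) and they disagree at SD 1.05 (25.7% against 32.0%).
- d = 0.25 L: SD 1.43 to 1.58. The smallest half-width, at CO 8, is 1.96 × 1.43/8 = 35.0%, so both readings fail at CO 5 to 8.
- d = 0: SD 1.90 to 2.11. The smallest half-width at CO 8 exceeds 46%, so both fail.

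**Step 5: scope.** The four parameters in the hypothesis can be set against the text. CO has the parenthesis as support for 30%. Stroke volume and heart rate are in both aims but have no support for 30%. Blood pressure has no support, is in neither aim and has no described reference. The 32% in Background names no parameter, so it does not fill these gaps.

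**The case against.** A careful analyst would narrow the choice. Because the plan puts bias inside the LOA, the literal reading is that both limits must fall within ±30%, so the larger one governs; the main rival is the half-width. That is right, and it reduces the dispute to two readings. A reader might infer a wider one, by also counting the more favourable limit or the full width. Judging agreement by the more favourable limit alone is not credible, and nothing in the plan points to the full width, so neither is used in sizing the problem here.

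The size also rests on assumptions. The 0.5 L is called a limit of bias, not an expected difference, and Step 4 shows cases in which the choice changes no verdict. That stands: the documents do not show that the verdict will turn on the reading, only that it can.

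A reader might further infer that the trial's powered conclusion is undermined. The documents do not support this. The margin is a mean difference in litres and does not involve the MPD.

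In the other direction, it could be said that readers can recompute the MPD from the bias and SD. The plan says these will be evaluated; it does not promise to report them together with the mean of the two methods, which recomputation also needs. The ambiguity therefore remains.

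**Conclusion.** The concern holds in two parts. First, the MPD formula as written gives a pair of values for a one-value test. The two credible readings differ by |bias|/mean, which is 10.0 to 6.3 points at bias 0.5 L and assumed CO of 5 to 8 L/min, and at CO 6 they give opposite verdicts for SD 0.66 to 0.92 L. The ambiguity is certain from the text. The size is illustrative, because SD, mean CO and true bias are all assumed, and the readings agree when bias is small or SD is large. The correction factor does not remove the problem, since it has no stated form and is not in the analysis section.

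Second, the 30% threshold is supported for CO alone, and the blood-pressure part of the hypothesis cannot be tested against echocardiography as described.

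Neither part affects the 1.0 L margin or the 38 per arm. A reader might also infer that the half-width is already known to be what the 30% benchmark means; the documents do not give the benchmark's definition, so that must be checked.

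**What to change.** 1. In both places in Statistical Analysis, replace the formula with a single-valued one: percentage error = 1.96 × SD of the differences / mean CO of the two methods. First check that the source of the 30% benchmark defines it this way; if it does not, use that source's formula and cite it.
2. Report bias separately with its confidence interval, and state whether it is judged against the 0.5 L or the 1.0 L figure in the sample-size paragraph, which gives both without saying how each applies.
3. In the hypothesis, limit the 30% criterion to CO. Report stroke volume and heart rate as bias and limits of agreement, or state a justified threshold for each.
4. Remove blood pressure from the NICOM-versus-echocardiography hypothesis unless a reference measurement is specified.

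The cost is wording in two sections and one source check; no extra patients are needed, and no extra data unless a blood-pressure reference is added. The downside is that stroke volume and heart rate lose a pass/fail criterion unless one is justified.
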